STUDY SUMMARY

Title of the clinical investigation

Evaluation of the feasibility of an expert patient decision-support system for optimizing the management of conditionally administered medications in a surgical ward

Short title

MORPHEE-2

Sponsor

Strasbourg University Hospitals

Principal Investigator

[name] [name]

HUS No.

8706

IDRCB No.

2022-A01926-37

Clinical Trial No.

NCT05707247

Rationale for the clinical investigation

The management of the numerous medications prescribed in connection with a surgical procedure represents a major challenge. Many new drugs are prescribed simultaneously, some of which are administered on an “as needed” basis, leading to a risk of suboptimal administration. The development of expert systems providing patient decision support represents a promising approach to improving perioperative medication management.

Primary Objective

To evaluate the feasibility of the INSAMED computerized decision-support tool regarding the administration of “as needed” medications after surgery.

Secondary Objectives

1. To evaluate the time to administration, according to current organizational practices, of medications prescribed on an “as needed” basis after surgery, in order to confirm the relevance of developing expert systems to improve current practice.
 2. To assess patient satisfaction with the therapeutic response provided as part of routine care.
 3. To assess patient satisfaction regarding the ease of use of the investigational device.
 4. To assess the safety of the recommendations generated by the computerized tool.
-

Primary Evaluation Criterion

Rate of concordance between the recommendations provided by the INSAMED computerized tool and those established by healthcare professionals.

Recommendations generated by INSAMED will be collected through extraction of the usage history from the digital interface (commercial smartphone) hosting the expert system.

Recommendations established by a healthcare professional based on a best-practice algorithm will be determined after receipt of an activation message from the device: a research nurse (RN) will generate a recommendation based on the medical algorithm for symptom management, medical prescriptions, and patient interview, without consulting INSAMED.

Secondary Evaluation Criteria

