Statistical analysis will include an initial descriptive phase (mean, median, standard deviation, and interquartile range for quantitative data; counts and percentages for qualitative variables).

Analysis of the primary endpoint will consist of evaluating concordance between the application's recommendation and that of the research nurse. As these are repeated binary data, concordance will not be assessed using a kappa coefficient, but rather through calculation of an intraclass correlation coefficient (ICC) derived from a mixed-effects logistic regression model with a random subject effect. Residual variance will be indirectly estimated using the methods described by Chakraborty et al.

The ICC will be reported with its 95% confidence interval, without formal hypothesis testing, as this is a pilot study.

Projected Timeline

- **Inclusion period duration:** 12 months
- **Participation duration per subject:** 2 days to a maximum of 2 months
- **Total study duration:** 14 months
- **Exclusion duration:** Not applicable

End of the research

The end of the research corresponds to the last visit of the last subject participating in the study.

Version 1.2 dated 20/12/2022, approved by the CPP Île-de-France II on 09/01/2023 and submitted to the ANSM on 13/01/2023

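### The primary endpoint is a concordance rate, but the only estimate planned with a confidence interval is a patient-level ICC, which does not measure that rate

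*Combined protocol and SAP*

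**What the plan says.** In the combined protocol and SAP, the Primary Evaluation Criterion is "Rate of concordance between the recommendations provided by the INSAMED computerized tool and those established by healthcare professionals". That is a proportion, and the section makes clear that the comparator is a research nurse who has not seen INSAMED's output.

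Statistical Methods states the same aim: "Analysis of the primary endpoint will consist of evaluating concordance between the application's recommendation and that of the research nurse". It then sets kappa aside ("As these are repeated binary data, concordance will not be assessed using a kappa coefficient") and replaces it with the "calculation of an intraclass correlation coefficient (ICC) derived from a mixed-effects logistic regression model with a random subject effect". On the residual term it says "Residual variance will be indirectly estimated using the methods described by Chakraborty et al". On reporting it says "The ICC will be reported with its 95% confidence interval, without formal hypothesis testing, as this is a pilot study".

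The section does not say what the model's binary outcome is, and it names no effect for rater or for activation. The only other route to a percentage is the opening descriptive phase, which promises "counts and percentages for qualitative variables" without naming concordance.

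**The concern.** A rate of concordance answers how often the tool and the nurse make the same recommendation. An ICC from a model whose only named random effect is the patient answers how much of the variation lies between patients. These are different quantities, and the second need not follow the first.

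The trial has no hypothesis test, so the estimate and its interval are the whole primary result. If that estimate does not measure agreement, the feasibility objective is judged on the wrong number. Two tools of very different quality could carry the same headline figure, and a tool that always matched the nurse could be reported with a low one.

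**Working it through.** **Figure in the plan.** The only number stated is 30 patients with at least one activation (60 targeted for inclusion). It rests on an empirical rule, with no rate, precision or power behind it, so there is nothing to reproduce. The check is whether the ICC tracks the endpoint.

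**Inputs.** From the documents: 30 patients, binary data, repeated measures, random subject effect only. Assumed, because the documents do not give them: activations per patient (1 to 8), the proportion of recommendations that are to give a medicine, how far a patient's need is similar from one activation to the next, and residual variance π²/3 (the cited method could not be consulted).

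**Formula.** ICC = σ²ₛ / (σ²ₛ + π²/3), where σ²ₛ is the between-patient variance on the logit scale, fitted by maximum likelihood with 40- or 41-point quadrature.

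**Reading 1: the outcome is concordant yes/no, one row per activation.** The concordance rate is governed mainly by the intercept, while the ICC uses only σ²ₛ.

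- Large sample, 4 activations each, true ICC 0.10: concordance rates of 50%, 80% and 95% gave ICCs of 0.10, 0.10 and 0.11. With true ICC 0.30, all three gave 0.30.
- 30 patients, geometric activations with mean 3, the same concordance probability in every patient: median ICC 0.00 at 95% concordance and 0.00 at 60%.
- 30 patients, 4 activations each, 95% concordance, true ICC 0.10: median 0.00, with 2.5th to 97.5th percentiles of 0.00 to 0.52. The ICC is also imprecise at this size.

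**Reading 2: the outcome is the recommendation, two rows (INSAMED and nurse) per activation.** The subject effect now absorbs two things at once: the two raters agreeing within an activation, and different activations of one patient resembling each other.

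Perfect agreement, 30 patients, need independent between activations (the ranges cover 50% and 80% of recommendations being to give):

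| Activations per patient | Median ICC |
|---|---|
| 1 | about 1 |
| 2 | about 0.5–0.6 |
| 3 | 0.25–0.40 |
| 4 | 0.2–0.3 |

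Large sample, 60% of recommendations to give:

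| True agreement | Clustering of need within patient | ICC at 2 activations | at 4 | at 8 |
|---|---|---|---|---|
| 100% | none | 0.52 | 0.20 | 0.09 |
| 100% | 0.3 | 0.71 | 0.49 | 0.39 |
| 80% | none | 0.28 | 0.11 | 0.05 |
| 80% | 0.3 | 0.41 | 0.28 | 0.23 |
| 50% (kappa 0) | 0.7 | 0.10 | 0.14 | 0.14 |

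At 4 activations, perfect agreement without clustering of need (0.20) scores below 80% agreement with clustering of 0.3 (0.28). The ordering of tools can therefore be reversed by a feature of the patients.

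**What the rate itself would offer.** Half-width = 1.96 × √[p(1−p) / n_eff], with n_eff = 30m / [1 + (m−1)ρ], where m is activations per patient and ρ is the within-patient correlation of concordance. For m = 3, ρ = 0.3, p = 0.8: n_eff = 90 / 1.6 = 56.2, and the half-width is 1.96 × √(0.16 / 56.2) = 10.5 percentage points.

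| m | ρ | p = 70% | p = 80% | p = 90% |
|---|---|---|---|---|
| 1 | any | ±16.4 | ±14.3 | ±10.7 |
| 3 | 0 to 0.3 | ±9.5 to 12.0 | ±8.3 to 10.5 | ±6.2 to 7.8 |
| 5 | 0 to 0.3 | ±7.3 to 10.9 | ±6.4 to 9.5 | ±4.8 to 7.1 |

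These are normal approximations with equal numbers of activations per patient. They are a planning guide only.

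**The case against.** Four points on the other side deserve weight.

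*The rate may still appear.* A reader might infer that concordance is never estimated. The documents do not support that. Concordant or discordant status is a qualitative variable, the Secondary Evaluation Criteria already use such a split for satisfaction, and the descriptive phase could produce its percentage. What stands is that this percentage is not named, has no interval and makes no allowance for clustering.

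*The ICC is not empty of agreement.* A reader might infer that it carries no information on agreement. That holds only under Reading 1. The wording of Statistical Methods fits Reading 2 at least as well; there the ICC reflects agreement in part, and with one activation per patient perfect agreement gives about 1. But Number of Subjects Required counts on repeated data, so the mixing remains.

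*The figures rest on assumptions.* They do. The activation count, clustering of need and residual variance are all assumed, and the ICC values move a good deal with them. A different residual variance rescales the ICC; it does not turn it into a rate. A reader might also expect a poor tool to be reported with an ICC near 1. That takes Reading 1 and a contrived mixture: with half the patients at 95% concordance and half at 5%, the median was about 0.96. Nothing in the documents makes such a mixture likely.

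*Avoiding kappa is defensible.* Ordinary inference for kappa assumes independent pairs, so the plan's caution is reasonable and should not be called an error. The narrower point stands: repeated data call for an interval that respects the clustering. They do not by themselves justify replacing an agreement measure with a subject-only ICC.

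**Conclusion.** The mismatch is real and should be corrected before analysis. The endpoint is a rate, the only quantity planned with an interval is a subject-level ICC, and under neither reading of the undefined outcome does that ICC estimate the rate. Under Reading 1 it does not distinguish 95% from 60% homogeneous concordance. Under Reading 2, a tool in perfect agreement can score anywhere from about 1 down to 0.09 (8 activations, no clustering of need), depending on how often patients use the device and how stable their needs are.

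The mismatch itself follows from the text and needs no assumption. The sizes are conditional on the assumed activation counts, clustering and π²/3, and are not predictions of what this trial will report.

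**What to change.** 1. Define concordance for each activation: what counts as the same recommendation from INSAMED and from the research nurse.
2. Make the primary estimate the proportion of concordant activations, with a 95% interval that allows for clustering by patient. An intercept-only GEE with small-sample robust variance, or a patient-level bootstrap, would serve.
3. Keep the ICC only as a description of clustering, and state the model's outcome and the residual-variance formula.
4. Optionally, add a chance-corrected coefficient with a patient-bootstrap interval.

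The cost is rewording about two paragraphs of Statistical Methods and a little more programming. No extra patients or data are needed.
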